## 15.2. ADVERSE EVENTS

Any adverse event having been reported during the study for a given subject will be classified by Preferred Term and corresponding System Organ Class using the MedDRA terminology.

The **occurrence** of an adverse event is defined by the appearance of a new single event, the reappearance of a previously recovered event or the worsening of a continuous event in severity or seriousness relative to its previous status (see Appendix 2).

An adverse event will be classified as:

- Pre-Treatment adverse event if it occurs or worsens strictly before the first study treatment administration
- Treatment emergent adverse event (TEAE) if it occurs during the treatment period (i.e. from first treatment administration date up to last administration date + 30 days included) or that worsens during the treatment period. Any new serious event that starts > 30 days after treatment discontinuation and is assessed by the Investigator as related to study treatment will be also considered as TEAE.

A Related TEAE (to a specific study drug) is defined as a TEAE with relationship to the study treatment assessed by the investigator as “Suspected” for this drug.

A Related TEAE (to any drug) is defined as a TEAE with relationship to the study treatment assessed by the investigator as “Suspected” for ENCORAFENIB or BINIMETINIB or CETUXIMAB.

An adverse event leading to study drug discontinuation (for a specific study drug) is defined as an adverse event with Action Taken with Study Treatment reported as “DRUG WITHDRAWN” for this drug.

An adverse event leading to study treatment discontinuation is defined as an adverse event with Action Taken with Study Treatment reported as “DRUG WITHDRAWN” for ENCORAFENIB or BINIMETINIB or CETUXIMAB.

An adverse Event leading to dose reduction or study drug interruption (for a specific study drug) is defined as an adverse event with Action Taken with Study Treatment reported as “DOSE REDUCED” or “DRUG INTERRUPTED” for this drug.

An adverse Event leading to dose reduction or study treatment interruption is defined as an adverse event with Action Taken with Study Treatment reported as “DOSE REDUCED” or “DRUG INTERRUPTED” for ENCORAFENIB or BINIMETINIB or CETUXIMAB.

An adverse event requiring a corrective treatment or procedure is defined as an adverse event with the box “yes” ticked for either Corrective Treatment or Corrective procedure.

Missing severity or relationship to the study treatment will not be substituted.

Missing or incomplete dates will be imputed for the calculation of TEAE as described in section 11.2.4, but will be presented as reported in the CRF in the data listings.

A summary table will be produced giving the number of:

- Subjects with at least one AE
- Subjects with at least one TEAE
- Subjects with at least one related TEAE

- Subjects with at least one AE leading to study treatment discontinuation (at least one study drug)
- Subjects with at least one AE leading to study drug discontinuation (respectively: binimetinib, encorafenib, cetuximab)
- Subjects with at least one related AE leading to study treatment discontinuation (at least one study drug)
- Subjects with at least one AE leading to discontinuation of binimetinib and encorafenib
- Subjects with at least one related AE leading to discontinuation of binimetinib and encorafenib
- Subjects with at least one AE leading to discontinuation of all study drugs
- Subjects with at least one related AE leading to discontinuation of all study drugs
- Subjects with at least one AE leading to dose reduction or study treatment interruption (at least one study drug)
- Subjects with at least one related AE leading to dose reduction or study treatment interruption (at least one study drug)
- Subjects with at least one AE requiring a corrective treatment or procedure
- Subjects with at least one related AE requiring a corrective treatment or procedure
- Subjects with at least one Serious Adverse Event (SAE)
- Subjects with at least one Treatment Emergent Serious Adverse Event (TESAE)
- Subjects with at least one related TESAE
- Subjects with at least one Adverse Event leading to death

Associated number of occurrences will be provided for each case listed above.

The number and percentage of subjects with at least one AE having occurred before first study treatment administration (Pre-Treatment AEs) will be tabulated by MedDRA System Organ Class (SOC) and Preferred Term (PT).

### **Treatment Emergent Adverse Events**

Numbers and percentages of subjects with at least one reported TEAE will be tabulated:

- By MedDRA System Organ Class (SOC) and Preferred Term (PT), overall and maximum Grade 3 or higher

- By MedDRA System Organ Class (SOC), Preferred Term (PT), and maximum grade (Grade 1 to Grade 5)
- And by MedDRA System Organ Class (SOC), Preferred Term (PT), and worst outcome (from “Recovered” to “Fatal” as following: Recovered/Resolved, Recovered/Resolved with sequelae, Recovering/Resolving, Unknown, Not Recovered/Not Resolved, Fatal)

A subject with multiple occurrences of the same AE will only be counted under the maximum NCI-CTCAE v4.03 grade or worst outcome for this AE, depending on the analysis.

The number and percentage of subjects with at least one TEAE, and the number of occurrences of TEAEs, will be tabulated by MedDRA System Organ Class (SOC), Preferred Term (PT), and seriousness (by descending order of frequency).

The same analyses will be performed for TEAEs assessed as related to study treatment by the investigator, overall and by study drug.

Adverse Events related to COVID-19 pandemic will be listed on an individual basis: subject’s code, sex and age, Investigator's reported term, preferred term and LLT, NCI-CTCAE v4.03 grade, seriousness, onset day, date and time of the first study treatment administration, duration, relationship to study treatment, action taken regarding the study treatment administration, use of a corrective treatment, outcome, AE status with respect to treatment emergence (AE/TEAE). AEs related to COVID-19 are reported in the eCRF with a prefix “COVID19” and will be coded using appropriate MedDRA codes. Prefix will not be displayed in the listing.

#### **Onset day of TEAEs**

The number and percentage of subjects with at least one TEAE will be presented by MedDRA System Organ Class (SOC) and Preferred Term (PT), and the first onset day presented in classes ([D1-Week4], [week4-week12], [week12-week24], [week24-EOT], Safety Follow-Up, Long term Follow-Up). The onset day is calculated in section 9.1.3.

#### **Serious Adverse Events (SAEs)**

The number and percentage of subjects with at least one Treatment Emergent SAE (TESAE) will be presented by MedDRA System Organ Class (SOC) and Preferred Term (PT), overall and

maximum Grade 3 or higher. The same analysis will be performed for related TESAEs, overall and by study drug.

Serious adverse events will also be listed on an individual basis: subject's code, sex and age, Investigator's reported term, preferred term, NCI-CTCAE v4.03 grade, onset day, date and time of the first study treatment administration, duration, action taken regarding the study treatments administration, use of a corrective treatment, outcome and relationship to the study treatments in the Investigator's opinion, SAE status with respect to treatment emergence (SAE/TESAE).

#### **Adverse events leading to study treatment discontinuation or interruption**

The number and percentage of subjects with at least one AE leading to study treatment discontinuation will be presented by study drug, MedDRA System Organ Class (SOC) and Preferred Term (PT), overall and maximum Grade 3 or higher.

The same table will be provided for AEs having led to a study treatment interruption.

AEs having led to study treatment discontinuation will be listed, on an individual basis in the same way as serious adverse events previously described, during the study (from the date of the first study treatment administration onwards).

#### **Adverse events leading to dose reduction**

The number and percentage of subjects with at least one AE leading to dose reduction will be presented by study drug, MedDRA System Organ Class (SOC) and Preferred Term (PT), overall and maximum Grade 3 or higher.

#### **Adverse events requiring corrective treatment or procedure**

The number and percentage of subjects with at least one AE requiring corrective treatment or procedure will be presented by MedDRA System Organ Class (SOC) and Preferred Term (PT), overall and maximum Grade 3 or higher.

#### **Death**

The number and percentage of subjects with adverse event leading to death will be presented by MedDRA System Organ Class (SOC) and Preferred Term (PT) for:

- on-treatment deaths (occurring during the treatment period, as defined in section 9.1.2)
- deaths occurring > 30 days after the last study treatment administration

In addition, deaths will be also listed on an individual basis for:

- Patients who died within 30 days (included) after the last study treatment administration,
- Patients who died > 30 days after the last study treatment administration

AE analyses will be generated for the subgroup of subjects in Japan.

### **AEs of special interest (AESI)**

AEs of special interest are described in Appendix 3.

The MedDRA terms used to define the AESIs and the list of AESIs may be updated during the trial based on accumulating safety data.

Treatment emergent AESIs (TEAESI) will be presented by AESI grouping and PT, overall and maximum Grade 3 or higher.

The same analysis will be performed for related TEAESIs, overall and by study drug.

The number and percentage of subjects with at least one Serious TEAESI (TESAESI) will be presented by AESI grouping and PT, overall and maximum Grade 3 or higher. The same analysis will be performed for related TESAESIs, overall and by study drug.

TESAESIs will also be listed on an individual basis.

The number and percentage of subjects with at least one AESI leading to study treatment discontinuation will be presented by study drug, AESI grouping and PT, overall and maximum Grade 3 or higher.

The same table will be provided for AESIs having led to study treatment interruption.

AESIs having led to study treatment discontinuation will be listed on an individual basis.

The number and percentage of subjects with at least one AESI leading to the dose reduction will be presented by study drug, AESI grouping and PT, overall and maximum Grade 3 or higher.

The number and percentage of subjects with at least one AESI requiring corrective treatment/procedure will be presented by AESI grouping and PT, overall and maximum Grade 3 or higher.

The number and percentage of subjects dead due to an AESI will be presented by AESI grouping and PT.

### **Groupings of adverse events**

Such groups (see Appendix 3) consist of one or more AEs (MedDRA Preferred Terms) and for which there is a specific clinical interest regarding the study treatment.

Grouping of AEs will be summarized as follows:

- Overall summary of each grouping, including the number of subjects with at least one AESI of the grouping, at least one related AESI, at least one serious AESI, at least one AESI leading to study treatment discontinuation, at least one AESI leading to study treatment interruption, at least one AESI leading to dose reduction, at least one AESI requiring corrective treatment/procedure, and the associated numbers of occurrences.
- Number and percentage of subjects with at least one TEAESI by grouping and PT, and by maximum grade (Grade 1 to Grade 5).
- Number and percentage of subjects with at least one TEAESI by grouping and PT, and worst outcome

The onset day of first occurrence of any TEAESI from the grouping will be described by grouping and Preferred Term (PT), overall and maximum Grade 3 or higher.

For each grouping, the maximum duration of TEAESI occurrences for subjects with at least one TEAESI from the considered grouping will be also described by Preferred Term (PT), overall and maximum Grade 3 or higher. For the calculation of the duration, end date of TEAESI will be imputed according to rules described in section 11.2.4 (AE end dates).

All AEs will be included in the listings of individual data.

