10.2.2. Reporting of Serious and non-serious AEs

All AEs, serious and non-serious and regardless of causality to study drug (including the exacerbation of a pre-existing condition), will be fully recorded on the appropriate e-CRF. For each AE, the Investigator must provide its duration (start and end dates or ongoing), severity (intensity), assessment of causality and seriousness and whether corrective action or therapy was required and whether action was taken with regard to study drug treatment.

Any AE that occurs after the signing of the ICF should be recorded on the AE e-CRF page regardless the relationship with the study procedure. All AEs occurring from the first dose of study drug including the 30 days after the last dose of study (30-day follow-up period) drug must be recorded on the AE e-CRF regardless of the relationship with the study drug.

If an AE occurs more than once in the same subject during the study, each occurrence must be recorded as a separate AE.

Any SAE occurring from the signing of the ICF should be reported as an SAE regardless of the relationship with the protocol procedure or with study drug.

The investigator must notify the sponsor of this event by sending within 24 hours the "SAE Form", with all the available information about the event, to the sponsor's Corporate Vigilances e-mail dedicated box :

[contact]

In case it is not possible to send the report by e-mail it can be sent by fax to:

[name]

In addition, all SAEs must be recorded into the e-CRF.

Study disease progression (including malignant disease progression with fatal outcome), if documented by the use of appropriate method (as per protocol) will be reported as progression of study disease in the e-CRF (study end-point) and should NOT be reported as an SAE unless a causal relationship to study treatment is suspected.

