13.9.2. Adverse Events

Any AE reported during the study for a given subject will be classified by preferred term and corresponding system organ class using the MedDRA terminology.

The occurrence of an AE will be defined by the appearance of a new single event, the reappearance of a previously recovered event or the worsening of a continuous event (relative to its previous status).

A treatment emergent adverse event (TEAE) is defined as any event that first occurred during the treatment period (i.e. from first treatment administration date up to last administration date + 30 days) or that worsened during that study period.

Summary tables will display the number and percentage of subjects with TEAEs overall and by maximum grade, system organ class (SOC) and preferred term (PT). A subject with multiple occurrences of an AE will only be counted under the maximum NCI-CTCAE grade for this AE.

Similar analyses will also be performed for TEAEs assessed as related to study treatment by the investigator.

SAEs will also be described on an individual basis: subject's code, sex and age, Investigator's reported term, preferred term, date of the first study treatment administration, duration of each study drug, action taken regarding the study treatments administration, use of a corrective treatment, outcome and relationship to the study treatments in the Investigator's opinion.

Categories of adverse events of special interest (AESIs) will be considered. Such categories consist of one or more well-defined safety events which are similar in nature and for which there is a specific clinical interest in connection with the study drugs. These analyses will be specified in the SAP.

The number and percentage of subjects with at least one AE occurring before the first administration will be tabulated by MedDRA SOC and PT.

As per the EudraCT requirement: The number and percentage of subjects with at least one TEAE, and the number of occurrences of TEAEs, will be tabulated by MedDRA SOC, PT and seriousness (by descending order of frequency).

The same analysis will be performed for TEAEs assessed as related to study treatment by the investigator.

AE analyses will be generated for the subgroup of Japanese subjects.

All Adverse Events related to COVID-19 pandemic will be flagged in listings to assess any potential impact of the pandemic on the study integrity and subjects' safety. These Adverse Events will be reviewed by iDSMC.

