### 9.1.3. Durations and times

Some analysis may require the computation of a duration from a reference day to a post-reference day.

Duration will be defined in days (or in seconds, if applicable) as following:

- Duration (in days) = Date - Reference date + 1 day
- Duration (in seconds) = (DateTime) – (Reference DateTime) + 1 sec

Unless specified otherwise, durations of events (e.g., duration of treatment) will be calculated in days. Conversions to weeks, months, years will be days/7, days/30.4375, days/365.25, respectively.

The *onset day of AE* is calculated from the date of first study treatment administration up to the start date of the AE notification, as follows:

- If start date  $\geq$  Date of first administration: onset day = Date AE notification – Date of first study treatment administration + 1
- If start date  $<$  Date of first administration: onset day = Date AE notification – Date of first study treatment administration

*Study day* is defined in the following manner:

- On or after the start date of study treatment: the study day will be calculated as (date of safety assessment) – (start date of study treatment) + 1. Study day 1 will therefore be the first day of study treatment.
- Before the start date of study treatment: the study day will be calculated as (date of safety assessment) – (start date of study treatment).

*Time to event* is defined in the following manner:

- The time from event i to an event j (in days) will be calculated as (date of event j – date of event i) + 1

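### AESI duration is summarised per occurrence and each worsening starts a new occurrence, so a continuous AESI that worsens may be represented only by its longest piece

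*SAP*

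**What the plan says.** SAP 15.2, under Groupings of adverse events, states of AESI duration that "the maximum duration of TEAESI occurrences for subjects with at least one TEAESI from the considered grouping will be also described by Preferred Term". This is done overall and for maximum Grade 3 or higher. The onset day of the first treatment-emergent AESI is described for the same two rows. The only rule added there for duration is that missing end dates are imputed as in SAP 11.2.4.

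At the start of SAP 15.2, an occurrence may be a first appearance, and the definition also covers "the reappearance of a previously recovered event or the worsening of a continuous event in severity or seriousness relative to its previous status". Protocol 13.9.2 has the same rule without naming severity or seriousness.

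On recording, Protocol 10.2.2 says: "If an AE occurs more than once in the same subject during the study, each occurrence must be recorded as a separate AE". It also says: "For each AE, the Investigator must provide its duration (start and end dates or ongoing), severity (intensity), assessment of causality and seriousness". SAP 9.1.3 gives the formula: "Duration (in days) = Date - Reference date + 1 day".

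**The concern.** The occurrence rule is a sensible device for counting, because a worsening is worth counting. It does not carry over to duration. If an unbroken event is held as two or three records because it worsened, the maximum over records is the length of the longest stretch between worsenings, not the time for which the subject had the toxicity. The loss falls only on subjects whose event got worse.

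A reader of a table of maximum AESI duration will take it as how long the toxicity lasted. That matters for a triplet whose known toxicities Protocol 1.2.2 describes, for binimetinib, as mostly reversible and manageable. The documents name retinal groupings among the AESIs (SAP 15.10); the full list is in a separate file.

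**Working it through.** The plan states no figure for AESI duration, so there is nothing to reproduce. The check is whether the rules, applied together, return the length of a continuous event.

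**Inputs**
- Measure: maximum duration over treatment-emergent AESI occurrences, by grouping and preferred term (SAP 15.2, Groupings of adverse events).
- What starts a new occurrence: a new event, a recurrence after recovery, or a worsening (SAP 15.2; Protocol 13.9.2). An improvement does not.
- Recording: one AE per occurrence, each with its own dates and severity (Protocol 10.2.2).
- Formula: end date − start date + 1 (SAP 9.1.3).
- Joining rule: none found in SAP 9.1.3, 11.2.4, 15.2 or the readable part of Appendix 2.

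**Assumption.** The earlier record ends the day before the worsening, or on the same day (second figure where it differs).

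**Invented 60-day continuous event, days 1 to 60**

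| Pattern | Pieces (days) | Longest piece | Share of 60 days |
|---|---|---|---|
| No worsening, or improvement only | 60 | 60 | 100% |
| One worsening, on day 2 | 1, 59 | 59 | 98% |
| One worsening, midway | 30, 30 | 30 (31) | 50% (52%) |
| Two worsenings, evenly spaced | 20, 20, 20 | 20 (21) | 33% (35%) |
| 20 days Grade 1, 25 days Grade 2, 15 days Grade 3 | 20, 25, 15 | 25 (26) | 42% (43%) |

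**Second invented case.** Grade 1 on days 15 to 56 lasts 56 − 15 + 1 = 42 days. Grade 2 on days 57 to 84 lasts 84 − 57 + 1 = 28 days. The episode lasts 84 − 15 + 1 = 70 days and the rule returns 42, which is 42/70 = 60%.

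**Average under random timing (a further assumption).** If the worsenings fall uniformly within the episode, the expected longest of k pieces is (1/k) × (1 + 1/2 + … + 1/k) of the whole:
- One worsening, k = 2: (1/2)(1 + 0.5) = 0.75.
- Two worsenings, k = 3: (1/3)(1 + 0.5 + 0.333) = 0.61.

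**If the earlier record is left open to resolution.** In the 42 + 28 day case that record runs from day 15 to day 84, which is 70 days. The maximum is then the full length and nothing is lost.

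**With contiguous records joined first.** Every pattern in the table gives 60 days, and the second case gives 70.

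**The case against.** The strongest reply is that the mechanism needs a step the documents do not state: that the earlier record is closed when the worsening begins. The recording sentence in Protocol 10.2.2 reads naturally as being about recurrence, and the definition that includes worsening sits in the statistical sections, where it serves counting. The e-CRF completion guideline mentioned in Protocol section 7 is not available, and the Appendix 2 diagram is only partly readable. This stands as a limit on certainty. It does not remove the fault: with separate dated records the closing is the ordinary implication, and if practice varies between sites, the table mixes two measures.

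A reader might infer four stronger things that the documents do not support:
- *Any change of grade splits an event.* Only worsening does; an event that improves stays whole.
- *The reported durations are always too short.* Splitting acts downwards, but SAP 11.2.4 sets a missing end date to the cut-off date for ongoing events and to the last contact date for others, and moves partial dates towards the end of the month or year. These can lengthen durations, so the net direction is unknown.
- *The Grade 3 or higher rows will show low-grade data.* SAP 15.2 does not say whether that label selects subjects or records. If it selects subjects, a row could show the length of a Grade 1–2 piece and a Grade 1 onset day. This is an ambiguity, not a shown error.
- *The report would hide irreversible toxicity.* SAP 15.2 also tabulates AESIs by worst outcome and by discontinuation, interruption and dose reduction, and lists all AEs individually.

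It is also fair that the SAP names its measure openly as one of occurrences, and that SAP section 8 treats everything beyond the primary test as exploratory. That lowers the priority of the point.

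**Conclusion.** The point holds in a limited form. Where the earlier record is closed at the worsening, a continuous AESI that worsens is represented by its longest piece, and splitting understates its duration in the overall row.

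The illustrations (33% to 98% of true length in the 60-day patterns; averages of 75% and 61% under random timing) rest on invented events. Nothing in the documents says how often AESIs worsen, so no size can be given for this trial. The loss is also masked in a subject who has another, longer occurrence of the same preferred term. For an event present before treatment, starting the clock at the on-treatment worsening fits the treatment-emergent definition and is not part of the fault.

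This is a minor correction to a descriptive safety table. The primary endpoint and the subject counts by maximum grade are unaffected.

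**What to change.** In SAP 15.2, Groupings of adverse events:

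1. Keep the occurrence rule for counts.
2. For the overall duration row, join treatment-emergent records of the same preferred term that overlap or follow on within 1 day into one episode. Start the episode no earlier than the first treatment-emergent record, so that pre-treatment days are not added. Report the longest episode per subject.
3. For the maximum Grade 3 or higher rows, state that onset and duration come from the Grade 3 or higher records, not from lower-grade records of the same subject. Add a footnote that such a record may include a later lower-grade tail, because improvement does not start a new record.

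The cost is a few sentences in the SAP and a small derivation step, with no new data. If the derivation is not wanted, the least that would serve is to label the table as duration per occurrence.
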